Overall response will be evaluated beginning after 2 cycles of therapy. Objective response over the course of the study will be assessed by an IRF according to the IWG Revised Response Criteria for Malignant Lymphoma [1]. Patients, including those who achieve a CR, a PR, or stable disease (SD), may receive brentuximab vedotin for up to 16 cycles. Treatment with brentuximab vedotin beyond 16 cycles may be permitted at the joint discretion of the sponsor and the investigator for those patients experiencing continued clinical benefit. Following administration of the final dose of brentuximab vedotin, patients will be monitored for adverse events for a minimum of 30 days. Patients will be followed for PFS and OS every 12 weeks for 12 months after the EOT visit. Thereafter, assessment for OS will continue every 6 months until the sooner of death or study closure or a maximum of 2 years after enrollment of the last patient. Patients who remain on treatment after Cycle 16 will be followed according to the above schedule or until study closure.

Study drug will be discontinued due to occurrence of unacceptable AE, progressive disease, patient withdrawal, or study termination. Patients may discontinue therapy at any time. Additionally, those patients who experience a CR and are candidates for hematopoietic stem cell transplantation must discontinue brentuximab vedotin prior to chemotherapy and transplant; these patients will be followed for survival analyses until study closure.

AEs will be assessed, and laboratory values, vital signs, and electrocardiograms (ECGs) will be obtained to evaluate the safety and tolerability of brentuximab vedotin.

Serial blood samples for determination of the concentration of brentuximab vedotin, total therapeutic antibody, and MMAE will be obtained during Cycle 1 and subsequent cycles at prespecified time points as described in the Schedule of Events (SOE) in the protocol.

Radiological evaluations, (CT scan or magnetic resonance imaging [MRI], and PET as clinically indicated), will be employed to assess the status of the patient's underlying disease. An evaluation of disease response will be assessed by an IRF according to the IWG Revised Response Criteria for Malignant Lymphoma [1] evaluated at Cycles 2, 4, 7, 10, 13, and 16 and

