### 7.8.2 Secondary Efficacy Endpoints

Besides response rates per IRF, response rates (ORR, CR, PR) per investigator assessments will also be summarized for all 7 groups listed in Section 7.1. Response rates will be summarized with 2-sided 95% exact confidence intervals.

The other secondary efficacy endpoints include time to progression (TTP), time to response, duration of response (DOR), event-free survival (EFS), progression-free survival (PFS), and overall survival (OS). TTP, DOR, EFS, and PFS will be estimated using independent review facility (IRF) assessment unless otherwise specified. Time to response and DOR will be

summarized using the response-evaluable population; TTP, EFS, PFS, and OS will be summarized using the safety population.

TTP is defined as the time from the first dose until the first subsequent documentation of objective tumor progression. TTP will be censored on the last radiological assessment of measured lesions documenting absence of PD for patients who do not have objective tumor progression.

Time to response is defined as the time from the first dose until the first documentation of objective tumor response (CR or PR). Time to response will be censored on the last radiological assessment of measured lesions documenting absence of CR or PR for patients who do not have a CR or PR.

Duration of response in subjects with response (CR or PR) is defined as the time from start of the first documentation of objective tumor response (CR or PR) to the first subsequent documentation of objective tumor progression or to death due to any cause, whichever comes first. Duration of response will be censored on the day following the date of the last radiological assessment of measured lesions documenting absence of PD for patients who do not have objective tumor progression and are still on study at the time of analysis, are given antitumor treatment other than the study treatment or stem cell transplant (SCT), or are removed from study prior to documentation of objective tumor progression.

EFS is defined as the time from the first dose until any cause of treatment failure: disease progression per IRF (including progression events during follow-up period), premature discontinuation of treatment for any reason (ie, not completing 16 cycles of treatment due to any reason), or death due to any cause, whichever occurs first. EFS will be censored on the last PFS assessment date if none of the above events occur during the study.

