PFS is defined as the time from the first dose until disease progression or death due to any cause, whichever occurs first. PFS will be censored on the day following the date of the last radiological assessment of measured lesions documenting absence of PD for patients who do not have objective tumor progression and are still on study at the time of analysis, are given antitumor treatment other than the study treatment or SCT, or are removed from study prior to documentation of objective tumor progression. Patients lacking an evaluation of tumor response after their first dose will have their event time censored at the day of first dose.

OS is defined as the time from the first dose until death due to any cause. In the absence of confirmation of death, survival time will be censored at the last date the patient is known to be alive. Patients lacking data beyond the day of first dose will have their survival time censored at the day of first dose.

TTP, time to response, DOR, EFS, PFS, and OS will be analyzed using the Kaplan-Meier method, the 25th, 50th (median), and 75th percentiles, if estimable, will be presented along with the associated 2-sided 95% confidence intervals. The results will also be presented in figures (Kaplan-Meier plots).

A waterfall plot may be used to compare PFS per investigator from the current study versus PFS achieved with the last therapy received prior to study entry.

A waterfall plot will be used to summarize the greatest percent reduction in target lesions for individual patients.

Efficacy data will also be listed by patient.

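### PFS and DOR count deaths without time limit while progression-free survivors leave at their last scan, so deaths in OS-only follow-up bias the late curves downward

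*SAP*

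**What the plan says.** Section 4.4 sets two follow-up phases after treatment. In the first, "Patients will be followed for PFS and OS every 12 weeks for 12 months after the EOT visit". In the second, "Thereafter, assessment for OS will continue every 6 months until the sooner of death or study closure", with an outer limit of 2 years after the last patient is enrolled.

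Section 7.8.2 fixes the endpoints. For PFS, "PFS is defined as the time from the first dose until disease progression or death due to any cause, whichever occurs first". DOR runs from first response "to the first subsequent documentation of objective tumor progression or to death due to any cause, whichever comes first". Neither definition sets a maximum interval between the last scan and a death that counts.

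For patients without progression, "PFS will be censored on the day following the date of the last radiological assessment of measured lesions documenting absence of PD". This covers those still on study at the analysis and those who "are given antitumor treatment other than the study treatment or SCT, or are removed from study prior to documentation of objective tumor progression". DOR has the same censoring rule. EFS counts progression, failure to complete 16 cycles, or death, and otherwise censors at the last PFS assessment.

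Sections 7.1 and 7.8.2 commit to Kaplan-Meier estimates with the 25th, 50th and 75th percentiles and plots, for seven groups. The two disease groups have a target of at least 15 evaluable patients each.

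**The concern.** Counting death as a PFS event is normal. The fault is that deaths and survivors are observed over different periods. Once scheduled PFS follow-up is over, progression is no longer sought but death still is. Take two patients who both reach that point progression-free and untreated. The one who stays alive leaves the risk set the day after the last scan. The one who dies a year later remains at risk until death and is an event. Membership of the late risk set thus depends on a future death. That is informative censoring, and it pulls the late curve down at any sample size.

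In small groups the effect is conspicuous. The median and 75th percentile of PFS or DOR could be set by one death long after the last scan, and a reader would take that figure as a measure of disease control. EFS has the same weakness, but only in patients who completed 16 cycles, because stopping earlier is already an EFS event.

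**Working it through.** **Plan's own figure.** The SAP gives no precision figure for PFS or DOR. Its only one, the exact 95% interval for 10 responders of 15, reproduces: 38.4% to 88.2% against the stated 38% to 88%.

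**Length of the gap.** Section 4.4 says patients "may receive brentuximab vedotin for up to 16 cycles" of 21 days each.
- Treatment: 16 × 21 = 336 days; 336 / 30.4375 = 11.0 months.
- End of scheduled PFS follow-up for a patient who completes 16 cycles: 11.0 + 12 = 23.0 months, ignoring delays and treatment past Cycle 16.
- Let A be the months from a patient's enrollment to the last patient's enrollment (not given in the SAP), and count first dose as enrollment. OS follow-up can run to A + 24 months.
- OS-only time is then up to A + 24 − 23 = A + 1 months. For a patient whose EOT is at 4 months (assumed) it is up to A + 24 − 16 = A + 8 months.

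**Effect of one death.** Illustrative arm of 15, assumed data: six progressions from 1.4 to 9.0 months, eight survivors censored at scans from 12 to 23 months, and one progression-free patient with last scan at month 22 who dies at month 36. That death is observable if A is at least 36 − 24 = 12 months. At each event time, S is multiplied by (1 − events / number at risk).

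| Case | S before month 36 | At risk at month 36 | S after | Median | 75th percentile |
|---|---|---|---|---|---|
| As written | 9/15 = 0.600 | 1 | 0.600 × (1 − 1/1) = 0 | 36 | 36 |
| Patient censored at last scan | 0.600 | 0 | stays 0.600 | not estimable | not estimable |
| As written, one survivor still scanned at month 40 | 0.600 | 2 | 0.600 × (1 − 1/2) = 0.300 | 36 | not estimable |
| As written, three progressions only | 12/15 = 0.800 | 1 | 0 | 36 | 36 |

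In the last row the 25th percentile is 36 months as well. With eight progressions, S is already 7/15 = 0.467 and the death cannot move the median, though it can still set the 75th percentile.

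**Rough frequency.** The SAP gives no hazards, so these figures are assumption-driven. Simulated trials of 15 assumed that half never progress and the rest have a median of 5 months, with EOT at 4 to 11 months, closure at 24 to 54 months and a non-progression death hazard of 0.3% or 1% per month. Share of trials in which the curve ends at zero:

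| Patients censored for other treatment | 0.3% per month | 1% per month |
|---|---|---|
| none | 31% | 64% |
| 30% | 24% | 52% |
| 60% | 15% | 32% |

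Different assumptions (24 months' accrual plus 24 months, hazards of 0.5% or 1% per month, 0% to 30% with later deaths not counted, 0% to 10% scanned to closure) gave 20% to 56%. If only deaths within PFS follow-up count, zero endings fall to about 1% to 6%, depending on how scan timing is modelled. A median that exists only because of late deaths appeared in about 9% to 25% of trials across all settings.

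**Direction of bias.** True 36-month PFS in the first set of assumptions is about 0.5 × exp(−0.003 × 36) = 45% or 0.5 × exp(−0.01 × 36) = 35%. With nobody censored for other treatment, the mean estimates as written were 37% and 21%.

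**The case against.** The strongest reply concerns scope and likelihood.

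- **Not every late death counts.** A reader might infer that any death at any later time is an event. The text does not support that: patients given other antitumor treatment or removed from study are censored at the last scan. The exposed group is those who remain progression-free, untreated and in OS follow-up. This stands, and the table above shows how far it lowers the frequency.
- **Not shown to be likely.** A reader might infer that in groups of 15 a distorted median is to be expected. Even at the top of the simulated range, 25%, three trials in four do not have one. The SAP offers no basis for any of the hazards. This stands.
- **Not always to zero.** Treatment and scans past Cycle 16 are allowed, so others may still be at risk. The drop is then partial, although in the example it still sets the median.
- **Transplant.** Patients who stop in CR for transplant are covered by the statement that "these patients will be followed for survival analyses until study closure". A reader might infer that their late deaths count as PFS events. The wording on SCT in the censoring rule can be read either way, and the chemotherapy before transplant might itself trigger censoring, so the point cannot be settled from the SAP.
- **Limited impact.** PFS and DOR are secondary and descriptive, and plots and listings would show a lone late death. That helps a careful reader but does not correct the reported percentiles.

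None of this removes the asymmetry. Section 7.8.2 itself sets the events and censoring, down to patients with no post-dose evaluation, so the missing rule belongs there.

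**Conclusion.** The point holds for patients in OS-only follow-up without progression, without other antitumor treatment and not removed from study. For them, being at risk after PFS follow-up depends on a later death, and the late PFS and DOR curves are biased downward. The direction follows from the SAP's own rules and needs no assumption beyond some such deaths occurring.

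The size is conditional. In a group of about 15, one late death can produce a sharp drop, to zero if that patient is the last at risk, and can set the median or 75th percentile. The frequencies rest on assumed death hazards, progression pattern, accrual and uptake of other treatment; they illustrate the problem and do not predict it. The primary ORR is unaffected. The definitions should be changed before analysis, but this does not threaten the trial's main conclusion.

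**What to change.** In section 7.8.2, for PFS and DOR, and for EFS in patients who completed 16 cycles:

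- Count death as an event only if it occurs on or before the end of the patient's scheduled PFS follow-up, that is 12 months after the EOT visit, or study closure if earlier.
- Otherwise censor at the last radiological assessment under the existing convention for that endpoint.
- Report the version that counts all deaths as a sensitivity analysis, with numbers at risk, and list the late deaths.

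The cut-off should be the end of PFS follow-up itself. A window after the last scan, such as 24 weeks, would still admit deaths after that point. For example, with survivors censored at month 23, a death at month 27 would still count. In the simulations such a window left zero endings in 7% to about 20% of trials.

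The cost is a few sentences and one extra run. A few late deaths leave PFS and DOR but remain in OS. The curves will also end earlier, so a late percentile may be reported as not estimable, which is what the data support. The change does not settle whether SCT triggers censoring; that wording needs its own clarification.

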## 7.0 METHODS OF ANALYSIS AND PRESENTATION

### 7.1 General Principles

In general, descriptive statistics (number of observations, mean, standard deviation (StdDev), median, minimum, and maximum) will be used to summarize continuous variables. Frequencies and percentages will be used to summarize categorical variables. Time-to-event data will be analyzed using the Kaplan-Meier method and results will be summarized by the 25th, 50th (median), and 75th percentiles, if estimable, with associated 2-sided 95% confidence intervals, as well as the percentage of censored observations.

Unless otherwise specified, safety and efficacy data will be summarized in the following 7 groups: 1.4 mg/kg phase 1 only; 1.8 mg/kg phase 1 only; 1.8 mg/kg phase 1&2 HL only; 1.8 mg/kg phase 1&2 sALCL only; 1.8 mg/kg phase 1&2 sALCL in first relapse only; 1.8 mg/kg all patients; all patients. Pharmacokinetic analyses will be summarized by dose and treatment cycle.

The baseline value is defined as the value collected at the time closest to, but prior to, the start of study drug administration, unless otherwise specified. A windowing convention will be used to determine the analysis value for a given study visit for observed data analyses.

All available efficacy and safety data will be included in data listings and tabulations. Data that are potentially spurious or erroneous will be examined under the auspices of standard data management operating procedures. In general, there will be no imputation of missing data. For time-related endpoints, subjects who have no specified events will be censored as specified for each respective endpoint in Section 7.8. Imputation rules for missing dates of AEs and concomitant medications are detailed in Sections 7.1.3 and 7.1.4.

SAS Version 9.2 (or higher) will be used for all analyses.

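### The PFS rule that censors unevaluated patients at the day of first dose carries no no-event condition, so read literally it removes a death before the first evaluation

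*SAP*

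**What the plan says.** SAP Section 7.8.2 defines the endpoint: "PFS is defined as the time from the first dose until disease progression or death due to any cause, whichever occurs first". The PFS paragraph closes with a rule for patients who were never evaluated: "Patients lacking an evaluation of tumor response after their first dose will have their event time censored at the day of first dose".

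Section 7.1 (General Principles) gives the general approach: "For time-related endpoints, subjects who have no specified events will be censored as specified for each respective endpoint in Section 7.8".

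Two other rules in Section 7.8.2 write the no-event condition into their own text. For EFS: "EFS will be censored on the last PFS assessment date if none of the above events occur during the study". For OS: "In the absence of confirmation of death, survival time will be censored at the last date the patient is known to be alive".

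PFS is summarized in the safety population (Section 7.8.2), which requires one dose of study drug (Section 7.2.1). The response-evaluable population also requires a postbaseline disease assessment (Section 7.2.4). Response evaluation begins after two 21-day cycles (Section 4.4).

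**The concern.** A patient who receives a dose and dies before any response evaluation meets both the event definition and the censoring sentence. The definition gives an event on the date of death. The sentence, taken by itself, gives a censored time of zero. Two programmers could follow the SAP in good faith and code this patient differently.

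The two codings do not err in opposite directions. Under the literal sentence the death leaves the PFS risk set before it can count, so PFS can only look better. OS and EFS would still count the same death. The groups are small, so a single patient would be visible in the curve. The choice might also be made only after such a patient is known, in an open-label study.

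Censoring a living patient with no evaluation at the day of first dose is not in question.

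**Working it through.** **1. Which patients are affected.** They have at least one dose, no post-dose evaluation, and a death. They are in the safety population and so in the PFS analysis. They cannot be response-evaluable. Their number, k, therefore cannot exceed the safety count minus the response-evaluable count, both of which the disposition table will report (Section 7.3).

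**2. Inputs.** Section 6.0 plans at least 15 evaluable patients per disease and at least 10 sALCL patients in first relapse. The SAP's only sample-size figure is the exact 95% interval for 10 responses in 15 evaluable patients, (38%, 88%). It reproduces as 38.4% to 88.2%. The point does not depend on that interval, but its use of response counts supports reading *evaluable* as response-evaluable. On that reading the affected patients come on top of the 15 or 10. The SAP gives no value for k; 0, 1 and 2 are assumed here.

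**3. Early PFS.** Let m be the number of evaluated patients, and let all k deaths come before any other event or censoring. Just after the deaths:

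- literal sentence: S = m/m = 100%
- definition: S = m/(m + k)

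| Group | m | k | Literal | Definition |
|---|---|---|---|---|
| Either disease | 15 | 0 | 100% | 100% |
| Either disease | 15 | 1 | 100% | 15/16 = 93.8% |
| Either disease | 15 | 2 | 100% | 15/17 = 88.2% |
| sALCL, first relapse | 10 | 1 | 100% | 10/11 = 90.9% |

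The same m patients remain at risk afterwards under both codings, so the definition curve equals the literal curve times m/(m + k) at every later time.

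**4. Reported percentiles.** The SAP reports the 25th, 50th and 75th percentiles. Take m = 15 and k = 1, with distinct later event times and no other censoring. After j later events:

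- definition: S = (15 − j)/16
- literal: S = (15 − j)/15

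A percentile is placed at the first event that brings S to the target or below. If S equals the target exactly, it is placed midway to the next event.

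| Percentile (target S) | Definition | Literal |
|---|---|---|
| 25th (0.75) | 12/16 at j = 3, exact: rank 3.5 | 11/15 at j = 4: rank 4 |
| 50th (0.50) | 8/16 at j = 7, exact: rank 7.5 | 7/15 at j = 8: rank 8 |
| 75th (0.25) | 4/16 at j = 11, exact: rank 11.5 | 3/15 at j = 12: rank 12 |

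Each percentile moves later by half an event.

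**The case against.** The strongest reply is that Section 7.1 already settles the matter. It says to whom the Section 7.8 censoring rules apply, namely subjects with no specified event. Death is a specified PFS event, so a patient who died is never a censoring case, and the two texts can be read together without conflict. Much of this stands: it is the better reading and probably the intended one. But Section 7.1 refers the reader to Section 7.8 for the rule itself, and the sentence found there is specific and unconditional. Nor does the SAP always leave the condition to Section 7.1, since the EFS rule and the first OS sentence write it out.

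A reader might infer more than the text supports, in three ways.

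- *That the SAP definitely censors these deaths.* It does not; the definition and Section 7.1 point the other way.
- *That other rules share the omission.* The main PFS rule ("PFS will be censored on the day following the date of the last radiological assessment of measured lesions documenting absence of PD") and the matching rule for duration of response carry further conditions beyond absence of progression: still on study at the analysis, given other antitumor treatment, or removed from study. The second OS sentence ("Patients lacking data beyond the day of first dose will have their survival time censored at the day of first dose") does not reach a later death, because a later death date is itself data beyond that day. None of these is a parallel omission.
- *That a PFS curve above the OS curve would prove an error.* A patient's own PFS time cannot exceed the OS time, but the Kaplan-Meier curves can cross under rules that are not disputed. For example, a patient censored for other antitumor treatment who later dies counts only in OS.

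It is also fair to say that the stakes are low. Efficacy data are listed by patient, and all deaths are listed (Section 7.11.1.3), so an affected patient could be found.

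**Conclusion.** The point holds as a minor wording defect. The sentence, followed literally, contradicts the PFS definition for a patient who dies unevaluated and biases PFS upward. Section 7.1 favours the correct handling without securing it.

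Per disease group, the size is 6.2 percentage points of early PFS for one such death (100 − 93.8) and 11.8 for two (100 − 88.2). For the 10 first-relapse sALCL patients it is 9.1 points for one death (100 − 90.9). These figures rest on an assumed k, on the planned evaluable counts being met exactly, and on the deaths preceding all other events and censoring. The percentile shifts also assume no other censoring. With k = 0 there is no effect.

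PFS is secondary and descriptive. The primary ORR, OS and EFS do not change under either reading.

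**What to change.** Limit the sentence to patients with no PFS event. Possible wording:

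> *Patients with no post-dose response evaluation and no PFS event are censored on the day of first dose. A death before any post-dose evaluation is a PFS event on the date of death, unless other antitumor treatment was started first; in that case the censoring principle of the main PFS rule applies.*

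The last clause is needed. Without it, an unevaluated patient who moved to other treatment and died during long follow-up would count as a PFS event, while an evaluated patient in the same position would be censored.

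The cost is one clause in the SAP and one condition in the PFS program. Death dates are already needed for OS. PFS may look slightly less favourable. If the sponsor already intends the Section 7.1 reading, deaths before any other antitumor treatment are coded as intended and the wording only secures this.
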